15.2. SECONDARY EFFICACY

All secondary efficacy analyses will be performed using both the FAS and the PPAS.

15.2.1. SRI RESPONSE

Systemic Lupus Erythematosus Responder Index (SRI) response will be assessed for Study Days 22, 43, 64, 85, 106, and 127, with Day 85 specified as the secondary endpoint for the study.

Document: SGN35-022 SAP v1 V0.3
Author: [REDACTED]

Version Number: 1.0
Version Date: 31Jan2017

Template No: CS_TP_BS016 – Revision 3
Effective Date: 01Apr2016

Reference: CS_WI_BS005

[REDACTED]

15.2.1.1. DERIVATION

The SRI definition of response includes meeting all of the following criteria:

- Reduction from baseline in SLEDAI of at least 4 points;
- no new British Isles Lupus Assessment Group (BILAG) A organ domain scores, relative to baseline
- no more than 1 new BILAG B score, relative to baseline;
- no worsening (increase of < 10% of scale length) in PhGA, relative to baseline.

Assessment for response will be made using data only for the visit of interest and baseline, without regard for changes at prior on-treatment visits.

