### **5.7.2      Allowed Medications**

If taking the following medications, the subject must be on a stable dose prior to the baseline visit for at least the durations indicated and be willing and able to continue at stable doses throughout the study:

- corticosteroids (up to 40 mg/day prednisone or equivalent): 4 weeks;
- hydroxychloroquine or other antimalarials: 3 months;
- mycophenolate mofetil, mycophenolic acid, azathioprine, methotrexate, leflunomide, or 6-mercaptopurine: 3 months;
- NSAIDS and COX-2 inhibitors at or below the maximum approved dose: 2 weeks; or
- Oral, injected, or implanted hormonal methods of contraception, as well as HRT: 3 months.

Temporary increases in corticosteroid dosage (“bursts”) are permissible during the study as follows.

- The maximum duration of a burst is limited to 14 days duration on no more than 2 occasions.
- The corticosteroid dose must return to the preburst dose or lower at least 1 week before the 12-week assessments.
- The maximum dosage during a burst is up to 0.5 mg/kg prednisone, or equivalent, including any other steroids being given.

- The specific dose and taper schedule is at the discretion of the Investigator.

No increases in corticosteroid dosage outside of bursts are permitted. Decreases in the maintenance corticosteroid dose are allowed.

MMAE is primarily metabolized by cytochrome P450 enzyme 3A4 (CYP3A4), and is a substrate of P-glycoprotein (P-gp). Caution should be used in co-administering drugs which strongly inhibit CYP3A4 or P-gp, since increased MMAE exposures may result.

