#### **6.2.3.2 Secondary**

The secondary endpoint is the proportion of subjects achieving an SRI response at Day 85.

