15.3.1. BILAG 2004

The BILAG disease activity index is assessed and scored by trained study investigators based the past 4 weeks of patient experience. Scoring is performed for each of the following domains: constitutional, mucocutaneous, central nervous system, musculoskeletal, cardiovascular/respiratory, abdominal, renal, ophthalmic and haematological. A total score will be derived from the nine domains by the investigator, as the maximum severity across the domains. No programmatic derivation is required for the index itself. BILAG scores are graded as follows: Grade A represents very active disease; Grade B represents moderate disease activity; Grade C

indicates mild stable disease; Grade D indicates no disease activity; Grade E indicates no current or previous disease activity.

No numeric scores will be assigned to the grades for any analyses.

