15.3.2. BICLA RESPONSE

15.3.2.1. DERIVATION

The BILAG-based Combined Lupus Assessment (BICLA) definition of response includes all of the following:

- BILAG-2004 improvement (all A scores at baseline improved to B/C/D, and all B scores improved to C or D);
- no worsening in disease activity (no new BILAG-2004 A scores and ≤ 1 new B score);
- no worsening of total SLEDAI-2K score from baseline (no change or reduction from baseline);
- no significant deterioration (< 10% worsening) in 100 mm visual analogue PhGA;
- no treatment failure (See Section 15.3.15)

Patients' BICLA response will be derived from the above criteria for visits on which all of the component variables are captured.

Document: SGN35-022 SAP v1 V0.3
Author: [REDACTED]

Version Number: 1.0
Version Date: 31Jan2017

Template No: CS_TP_BS016 – Revision 3
Effective Date: 01Apr2016

Reference: CS_WI_BS005

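### Day 85 SRI takes no account of rescue steroids: a permitted burst can fill half of the BILAG look-back, and the subject can still count as a responder

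*SAP*

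**What the plan says.** Protocol 6.2.3.2 names one secondary efficacy endpoint: "The secondary endpoint is the proportion of subjects achieving an SRI response at Day 85". SAP 15.2.1.1 requires four things for a response:

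- "Reduction from baseline in SLEDAI of at least 4 points";
- no new BILAG A domain score;
- "no more than 1 new BILAG B score, relative to baseline";
- no worsening in PhGA.

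It then adds: "Assessment for response will be made using data only for the visit of interest and baseline". The rest of that sentence sets aside what happened at earlier visits on treatment. The SRI definition in protocol 6.2.2 has no medication component either.

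Protocol 5.7.2 permits temporary corticosteroid increases of at most 14 days, on at most two occasions. The dose must be back at the preburst level or lower "at least 1 week before the 12-week assessments". No minimum gap between bursts is stated. SAP 15.3.1 says that BILAG is scored "based the past 4 weeks of patient experience".

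Rescue does count elsewhere. SAP 15.3.13 makes increased corticosteroids a treatment failure. The BICLA list in SAP 15.3.2.1 ends with "no treatment failure (See Section 15.3.15"), although 15.3.15 is the SF-36 section and treatment failure is defined in 15.3.13. Increased prednisone is also a SELENA flare criterion in SAP 15.3.8.

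**The concern.** A subject who worsens, receives a permitted burst and looks better at Day 85 can be a SELENA flare and a treatment failure under SAP 15.3.13. Once its cross-reference is read as intended, BICLA makes the same subject a non-responder. That subject can still be an SRI responder. The SRI comparison then mixes the effect of study drug with the effect of added steroid, and nothing in the planned output separates them:

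- The FAS analysis takes all randomized subjects as they are.
- The per-protocol set removes protocol violations, and a permitted burst is not one.
- The steroid analysis in SAP 15.3.12 records oral use as present or absent per visit interval. Background prednisone up to 40 mg/day is allowed (protocol 4.4.1 and 5.7.2), so a burst in a subject already on steroids does not show.

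The study is meant to inform a larger efficacy trial (protocol 8.1). A reader of the SRI result should be able to see whether it depends on rescue.

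**Working it through.** The plan gives no power, response rate or burst rate, so it has no figure to reproduce. The allocation agrees with itself: 10 per cohort at 4:1 gives 8 + 2, and four cohorts give 8 per dose and 4 × 2 = 8 placebo.

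**Step 1: days.** Inputs are the 28-day BILAG look-back (SAP 15.3.1), the 14-day maximum burst and the 7-day return rule (protocol 5.7.2).

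- Look-back for a Day 85 visit: Days 57-84 (or 58-85 if the visit day is counted).
- Latest return to the preburst dose: Day 85 − 7 = Day 78. The last burst day is Day 77 and the first is Day 77 − 13 = Day 64.
- Overlap: 14 of 28 days = 50%. Visits on Day 83 or 87, the ends of the ±2-day window, give the same result.
- Because no gap is stated, an immediately preceding burst (Days 50-63) adds Days 57-63, giving 14 + 7 = 21 of 28 days (75%). With a one-day gap and the visit day counted, the total is 19 of 28 (68%). With a 7-day gap it falls back to 14.

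**Step 2: what this touches in SRI.** BILAG enters only as a no-worsening condition, so there a burst can hide a new A or B score. The improvement condition is the SLEDAI fall, whose look-back the documents do not give. A burst may contribute to that fall, but the 50% figure does not measure it.

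**Step 3: weight of one subject.** 1/8 = 12.5 points. Hypothetical counts, two-sided Fisher's exact test:

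| Reclassified subject | Before | After |
|---|---|---|
| One placebo responder | 6/8 vs 2/8, p = 0.132 | 6/8 vs 1/8, p = 0.041 |
| One active responder | 6/8 vs 1/8, p = 0.041 | 5/8 vs 1/8, p = 0.119 |

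**Step 4: direction, under assumed rates.** Let p be the response rate without bursts, b the share of would-be non-responders given a burst, and s the share of those converted to SRI response. The observed rate is p + (1 − p) × b × s. Take p = 60% active and 20% placebo, a difference of 40 points.

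- b = 10% active, 30% placebo, s = 25%: active 0.60 + 0.40 × 0.10 × 0.25 = 0.61; placebo 0.20 + 0.80 × 0.30 × 0.25 = 0.26; difference 35 points.
- b = 10% active, 50% placebo, s = 100%: 0.64 and 0.60; difference 4 points.
- b = 30% active, 10% placebo: s = 25% gives 0.63 − 0.22 = 41 points; s = 100% gives 0.72 − 0.28 = 44 points.

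Across the first two settings, exact Fisher power at 8 vs 8 falls from 24% to between 18% and 2%. It is low even without bursts.

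**The case against.** **Counting outcomes regardless of permitted rescue is a recognised treatment-policy choice, and the SAP follows the protocol's SRI in having no rescue clause.** This stands, and it is why the SRI derivation should not be changed. However, neither document states or justifies that choice, and the SAP takes the opposite line for BICLA.

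**Rescue is already limited and reported.** Bursts are capped in length, number and dose. A worsening that calls for a significant change in therapy leads to withdrawal (protocol 4.4.4). Flares, time to treatment failure and steroid use are all analysed. This is true, but none of these outputs shows how many Day 85 SRI responders had a burst.

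**The look-back can also count against the subject.** With a burst on Days 64-77, Days 57-63 precede it, so the worsening that prompted the burst may be scored as a new A or B and block response. This stands: the window can help or hurt.

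Three stronger readings are tempting, and the documents do not support them.

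- A reader might take the SAP sentence on baseline and the visit as an instruction to ignore rescue. Read in full, it concerns changes at earlier visits. The gap comes from the list of components.
- A reader might infer that placebo subjects receive more bursts and that the result is therefore biased toward no difference. No burst rates are given, and Step 4 shows either direction.
- A reader might want all treatment failures under protocol 6.2.2 recoded as SRI non-responders. That definition refers to treatment outside the protocol, so it may miss permitted bursts. It also includes premature discontinuation of study treatment, so withdrawals for toxicity under protocol 4.4.4 would become efficacy failures.

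**Conclusion.** The point holds in a limited form. Day 85 SRI has no medication criterion, and a permitted burst can occupy 14 of the 28 BILAG look-back days. A subject so treated can still be a responder if the SLEDAI and PhGA criteria are met. The day count rests only on the documents. The direction and size of any effect on the treatment comparison are unknown, and the shifts in Step 4 rest on assumed rates. What is certain is that one subject is worth 12.5 points in a group of 8.

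This affects interpretation and not a confirmatory test. The primary objective is safety, there is no primary efficacy endpoint, testing is nominal and the sample size rests on clinical judgment. It is a low-cost improvement, not a flaw that invalidates the analysis.

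**What to change.** Keep the SRI derivation and the burst rule as they are.

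1. In SAP 15.2.1.2, add one prespecified sensitivity analysis of Day 85 SRI. Count as a non-responder any subject with either of the following, and state the denominator:
   - a corticosteroid increase above the baseline dose, permitted bursts included, that overlaps the 28 days before the Day 85 visit;
   - new or increased immunosuppressive or antimalarial therapy by Day 85.
2. Show by arm the number of Day 85 SRI responders who had a burst.
3. Reconcile the two treatment-failure definitions. Protocol 6.2.2 limits failure to treatment outside the protocol or premature discontinuation of study treatment. SAP 15.3.13 counts any increased corticosteroid, adds death, and restricts withdrawal to adverse events or lack of efficacy.
4. Correct the BICLA cross-reference in SAP 15.3.2.1 from 15.3.15 to 15.3.13.

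The cost is SAP wording and one extra table. Protocol 5.7 already requires start and stop dates and changes in concomitant medication on the CRF; I assume that these entries include steroid dose. The downside is a somewhat lower response rate in the sensitivity analysis.

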15.2.1.2. ANALYSIS

The following analyses will be performed for all study days with Day 85 specified as the secondary endpoint, and all other visits falling under exploratory analyses.

The percentage of subjects demonstrating SRI Response will be presented by treatment with 95% CI using Wilson's score method (SAS PROC FREQ syntax: table response/binomial (wilson)). Comparisons between each active treatment group and placebo will be performed using Fisher's exact test (two-sided). The ratio of percentages (relative risk) for active to placebo will be presented for each dose level with corresponding 95% CI, based on the score method [Farrington] (SAS PROC FREQ syntax: table trta*response / relrisk(method=score equal)). Percentages with Wilson 95% CI will be plotted versus study day per treatment, with all treatments overlain.

Logistic regression of the log odds of SRI response on log2 dose level (mg/kg) will be performed. Placebo subjects will be treated as a having dose of 0 mg/kg. Based on this model, the estimate of the slope and odds ratio (OR) for a doubling of dose will be presented with 95% CI (based on the profile likelihood) and two-sided p-value (Wald test).

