## 4.0 INVESTIGATIONAL PLAN

### 4.1 Summary of Study Design

This is a multicenter, randomized, placebo-controlled, double-blind, multiple-ascending-dose study to evaluate the safety and tolerability of brentuximab vedotin in subjects with active SLE. Approximately 40 subjects in 4 dosing cohorts (10 subjects per cohort) are planned for study participation at approximately 20 study sites in the US. Subjects who meet inclusion and exclusion criteria will be randomly assigned in a 4:1 ratio within each dosing cohort to receive IV brentuximab vedotin or placebo every 3 weeks (Days 1, 22, 43, and 64) for a total of 4 doses. The following doses are planned for each ascending dose cohort:

[figure not shown]
- 0.3 mg/kg IV every 3 weeks for 4 doses;
- 0.6 mg/kg IV every 3 weeks for 4 doses;
- 1.2 mg/kg IV every 3 weeks for 4 doses; and
- 1.8 mg/kg IV every 3 weeks for 4 doses.

There will be a total of 10 subjects in each dose cohort with 8 subjects randomly assigned to each of the 4 brentuximab vedotin doses and 2 subjects to placebo (for a total of 8 placebo subjects overall). Initiation of enrollment at the next dose level will only commence after the final subject of each cohort has been evaluated at the Day 43 visit, and upon endorsement of the SMC following review of the safety data. Depending on the findings, the SMC may recommend additional enrollment of subjects at specific dose levels to better characterize the safety of a particular dose, or may recommend different dose regimens based on the emerging safety data. When available from each full cohort, the SMC will review all Day 85 safety data and may recommend that an already enrolled succeeding dose cohort be discontinued, or its treatment regimen truncated. Doses are not to exceed 1.8 mg/kg IV every 3 weeks or equivalent. Up to 20 subjects total may be enrolled via additional SMC-recommended cohorts for a total of up to 60 subjects.

Assessments for safety (including PML monitoring, see Section 6.3.3), efficacy, PK, and PD will be performed at the times indicated in the schedule of events (see [Table 3](#)). Following the last dose of study drug, there will be a 6-week observation period (through Day 106) and a follow-up visit will take place at Day 127.

A flowchart of the study design is presented in [Figure 1](#).

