### **5.3 Method of Assigning Subjects to Treatment Group**

Once the subject meets inclusion and exclusion criteria and has provided written informed consent, the study site will request the study medication assignment using the Interactive Web Response System (IWRS).

A total of 10 subjects in each dose cohort will be randomly assigned in a 4:1 ratio, resulting in 8 subjects assigned to each of the 4 brentuximab vedotin dose cohorts and a total of 8 subjects assigned to placebo (2 per cohort).

To randomly assign a subject to treatment, the study site will use the internet to access the IWRS. Subjects will be assigned their 6-digit subject number, starting with a 3-digit site number followed by a hyphen and a 3-digit sequential number (eg, 101-001). The IWRS will provide the study drug kit number(s) of the blinded study drug to be dispensed.

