### 8.2 Statistical Methods

Data will be analyzed by Quintiles Inc. biostatistical staff. All details regarding the statistical analysis and the preparation of tables, listings, and figures will be described in the Statistical Analysis Plan prepared by Quintiles and approved by the Sponsor before database lock.

Summaries for safety and efficacy data collected will be presented for each treatment group, ie, for brentuximab vedotin 0.3, 0.6, 1.2, or 1.8 mg/kg IV every 3 weeks and placebo at each scheduled visit/assessment. Placebo subjects across cohorts will be aggregated for analysis. Subjects will be evaluated according to the treatment received.

For qualitative parameters, the population size (N for sample size and n for available data) and the percentage (of available data) for each class of parameters will be presented. Quantitative parameters will be summarized by the population size (N for sample size and n for available data), the mean, the standard deviation, the median, 25th percentile, 75th percentile, the minimum, and the maximum values. Geometric means and coefficients of variation will be included as deemed relevant.

A nominal significance level of 5% will be used for exploratory inference testing.

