### **8.5.2 Secondary Analyses**

The number and percentage of subjects achieving SRI response will be presented with 95% exact binomial confidence intervals (CIs). Comparisons between the active treatments and placebo will be performed through a Fisher’s exact test. The nominal p-value and 95% CI for the treatment effect will be presented.

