15.3.8.2. ANALYSIS

The analysis for incidence of flares will replicate that performed for SRI, and will be performed for each severity grade (mild/moderate and severe) and overall.

The flare-free survival function will be estimated by treatment group and for all active-treated subjects combined using Kaplan-Meier methodology, with 95% confidence intervals based on Greenwood's formula. These survival curves will be plotted. The KM estimates of quartiles for time to event with the corresponding 95% CIs will be provided for each treatment and for all active-treated subjects, when estimable, using Greenwood's formula.

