15.3.10.2. ANALYSIS

The analysis for occurrence of renal flares will replicate that performed for SRI. Flare-free survival will be estimated as detailed for SELENA flares (Section 15.3.8.2).

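### For SRI and the endpoints that replicate it, the only planned direct contrast with placebo is a relative risk, which has no finite estimate when none of the 8 placebo subjects has an event; a risk difference should be added.

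*SAP*

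**What the plan says.** Protocol 8.5.2 sets the requirement for SRI: "The nominal p-value and 95% CI for the treatment effect will be presented". It does not name the effect measure.

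SAP 15.2.1.2 supplies the measure: "The ratio of percentages (relative risk) for active to placebo will be presented for each dose level", with a score-based 95% CI. The section also plans per-arm percentages with Wilson intervals, a two-sided Fisher's exact test of each dose against placebo, and a logistic regression on log2 dose that yields an odds ratio per doubling of dose. It plans no risk difference and has no rule for a placebo group without responders.

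The analysis is then reused by reference. SAP 15.3.8.2 states "The analysis for incidence of flares will replicate that performed for SRI" and SAP 15.3.10.2 states "The analysis for occurrence of renal flares will replicate that performed for SRI". Equivalent statements cover BILAG clinical response, BICLA, SLEDAI clinical response, ACR response, BILAG flares, active renal disease and corticosteroid use.

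On the comparator, Protocol 4.1 assigns in each cohort "2 subjects to placebo (for a total of 8 placebo subjects overall", and Protocol 8.2 adds "Placebo subjects across cohorts will be aggregated for analysis".

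**The concern.** A relative risk has the placebo proportion in its denominator. With so few placebo subjects, a count of zero is a realistic outcome for any uncommon endpoint. Because one pooled placebo group serves every comparison, a zero count removes the finite ratio for all four dose levels at that visit.

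The study exists to inform the design of a larger efficacy study (Protocol 8.1), and that calls for an effect size with a plausible range. If the planned measure fails, the team would have to choose a substitute after seeing the data.

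**Working it through.** **Inputs from the documents.** Protocol 5.3: "A total of 10 subjects in each dose cohort will be randomly assigned in a 4:1 ratio". There are four cohorts, so placebo = 4 × 10 × 1/5 = 8, which reproduces the plan's own total. Each dose group has 10 × 4/5 = 8.

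**Input that is assumed.** The true placebo rate is not given for SRI or for any replicated endpoint. A range of 5% to 40% is used.

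**Chance that the ratio has no finite estimate.** This is P(0 of n) = (1 − p)^n. For example, 0.9^8 = 0.430.

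| Assumed placebo rate p | n = 8 (planned) | n = 6 evaluable | n = 12 |
|---|---|---|---|
| 5% | 66% | 74% | 54% |
| 10% | 43% | 53% | 28% |
| 20% | 17% | 26% | 7% |
| 30% | 6% | 12% | 1.4% |
| 40% | 1.7% | 5% | 0.2% |

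The n = 6 column illustrates missing data, because SAP 15.1 bases percentages on subjects with available data. The n = 12 column applies if enrolment reaches 60 and the 4:1 ratio is kept, which is an assumption: 60/5 = 12.

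Solving (1 − p)^8 = 0.5 gives p = 0.083, and (1 − p)^8 = 0.1 gives p = 0.25. So with 8 placebo subjects the chance exceeds one half only below a rate of about 8%, and exceeds 10% only below about 25%.

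**What each measure gives when placebo is 0/8.** The Miettinen-Nurminen interval for the difference is the set of values d for which

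|p1 − p2 − d| ≤ 1.96 × √{[p̃1(1 − p̃1)/n1 + p̃2(1 − p̃2)/n2] × N/(N − 1)},

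where p̃1 and p̃2 are the maximum-likelihood proportions subject to p̃1 − p̃2 = d, and N = n1 + n2 = 16.

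- *0/8 against 0/8.* For d > 0, p̃2 = 0 and p̃1 = d. The limit solves d/(1 − d) = 3.84 × (1/8) × (16/15) = 0.512, so d = 0.34. The interval is −34 to 34 points.
- *4/8 against 0/8, upper limit.* Again p̃2 = 0, so (d − 0.5)² = 0.512 × d(1 − d), which gives d = 0.79. The lower limit, found numerically, is 0.08. The difference is 50 points (8 to 79), and Fisher's p = 0.077.
- *1/8 against 0/8.* The difference is 12.5 points (−24 to 48, found numerically).

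Without the N/(N − 1) factor, the first two intervals become −32 to 32 and 10 to 78 points. The conclusion does not depend on that choice.

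For the relative risk, the score interval (computed without that factor) keeps lower limits of 0.61, 1.34 and 2.16 when 2, 4 and 6 of 8 active subjects respond. In each case there is no finite estimate and no upper limit. At 0/8 against 0/8 the interval runs from 0 to infinity.

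**Whether the odds ratio fills the gap.** It does not. It is a slope across doses, not a contrast of one dose with placebo. The regressor is log2 dose with placebo set to 0 mg/kg, and log2(0) is undefined, so placebo subjects cannot enter the model without a convention that the SAP does not state.

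**The case against.** The best opposing case is that little is lost. With zero placebo events the reader still has each arm's percentage with its Wilson interval, the Fisher p-value, and a lower limit for the ratio if any active subject responds. For flares, active renal disease and corticosteroid use there are also Kaplan-Meier estimates with intervals. The point estimate of the risk difference follows by subtracting two displayed percentages. A relative risk with a CI satisfies Protocol 8.5.2, which names no measure. The study is exploratory, its primary objective is safety, and no decision rule rests on this estimate. Enlargement could also reduce the problem: "Up to 20 subjects total may be enrolled via additional SMC-recommended cohorts for a total of up to 60 subjects".

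All of that stands, and it limits the weight of the point. It does not supply the missing item, an interval for the size of the placebo contrast. Two per-arm intervals do not give one, and a lower bound alone does not bound the effect from above.

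The gain is also smallest for the rarest events. An interval of −34 to 34 points at 0/8 against 0/8 is finite but says little. In addition, the score interval can exclude zero while Fisher's test does not reach 5%, as at 4/8 against 0/8; the planned ratio interval behaves the same way, with a lower limit of 1.34.

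**Conclusion.** The point holds as a low-cost improvement. For SRI and the endpoints that replicate it, the relative risk is the only planned direct active-versus-placebo estimate. It fails whenever placebo has no events, for all doses at once, and no fallback is stated. With 8 placebo subjects the chance is 43%, 17%, 6% and 2% at assumed placebo rates of 10%, 20%, 30% and 40%.

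A reader might infer more than the documents support:

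- **That the ratio will often fail for SRI.** This depends on a placebo rate that is not given. At 30% to 40% failure is uncommon.
- **That zero placebo events is the likeliest result for flares or renal disease.** With n = 8, zero is the single likeliest count only if the rate is below 1/9 (11%), and no such rate is stated. Active renal disease may also be present at baseline, since the protocol plans analyses in those subjects.
- **That every binary endpoint is affected.** The 20/50/70% reductions in the global assessments, joint counts, HAQ-DI and ESR are only tabulated or summarized, without a relative risk.
- **That only a Fisher p-value would remain, or that the protocol is breached.** Neither is so, for the reasons given under the objection.

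**What to change.** In SAP 15.2.1.2, add that the risk difference (each dose level, and all active subjects combined, minus placebo) will be presented with a Miettinen-Nurminen score 95% CI, alongside the relative risk, for SRI and every endpoint whose analysis replicates it. State that the relative risk will be reported as not estimable when placebo has no events.

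Add a table note that the score interval and Fisher's test can disagree, and that the interval is wide when events are rare.

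The cost is about two SAP sentences, one further option in the same SAS procedure, and a two-level treatment variable for the pooled comparison. Nothing in Protocol 8.5.2 conflicts with it. It should be settled before unblinding, so that the fallback is not chosen after a zero count has been seen.
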